16.2. SECONDARY IMMUNOGENICITY

The analyses will be based on the PPS and ES.

16.2.1. SECONDARY IMMUNOGENICITY VARIABLES & DERIVATIONS

In order to assess the immunogenicity of Hib-components in terms of percentage of subjects above the thresholds for short-term ($\geq 0.15 \mu\text{g/mL}$) and long-term ($\geq 1.0 \mu\text{g/mL}$) protection as well as in terms of GMCs (post-primary, pre- and post-booster vaccination):

Document : \quintiles.net\enterprise\Apps\sasdata\SASb\SAS\GSK\Infanrix\PPD\Biostatistics\Documentation\NSAP

Author: PPD Version Number: 1.0

Version Date: [07JAN2021]

Template No.: CS_TP_BS016 Revision 6

Reference: CS_WI_BS005

[figure not shown]
Effective Date: 02Dec2019

- Descriptive analysis for each treatment group will be provided by country and maternal immunisation for anti-PRP antibody concentrations at 1-month post-primary vaccination, pre-booster and 1-month post-booster vaccination for the PPS and ES. This analysis will also be provided per subgroup for the PPS as per Section 7.5.
- GMC and its associated 2-sided 95% CI will be calculated on all subjects by treatment groups at 1-month post-primary, pre-booster and 1-month post-booster vaccination.
- The number and percentage of subjects with anti-PRP antibody concentrations $\geq 0.15 \mu\text{g/mL}$, $\geq 1.0 \mu\text{g/mL}$, $\geq 5.0 \mu\text{g/mL}$ at 1-month post-primary, pre-booster and 1-month post-booster vaccination with associated 2-sided 95% CI will be provided by treatment groups. [Clopper](#) and Pearson exact CI will be used for proportions.
- An adjusted GMC and GMC ratio with 2-sided 95% CI for treatment group which is derived from an ANOVA model on log10 transformed concentration will be tabulated for anti-PRP antibody concentrations. The model will include country, maternal immunisation and group as fixed effects.
- Reverse cumulative curves at each time point will also be displayed by treatment group for the ES and PPS.

16.2.2. MISSING DATA METHODS FOR SECONDARY IMMUNOGENICITY VARIABLE(S)

Missing data will not be replaced. Refer to Section 7.3.

16.3. TERTIARY IMMUNOGENICITY

Document : \\quintiles.net\enterprise\Apps\sasdata\SASb\SAS\GSK\Infanrix\PPD \Biostatistics\Documentation\n\SAP

Author: PPD Version Number: 1.0

Version Date: [07JAN2021]

Template No.: CS_TP_BS016 Revision 6

Reference: CS_WI_BS005

Effective Date: 02Dec2019

CCI

CCI

17. SAFETY OUTCOMES

All outputs for safety outcomes will be based on the ES.

There will be no statistical comparisons between the treatment groups for safety data, unless otherwise specified within the relevant section.

17.1. ADVERSE EVENTS

Adverse Events (AEs) will be coded using MedDRA central coding dictionary, Version 23.0 or higher.

Partial dates will be handled based on information available in [Appendix 2](#)

17.1.1. UNSOLICITED AEs, INCLUDING SAEs

For each study treatment, the incidence rates (frequencies and percentages) of subjects/events with unsolicited AEs, including serious AE, occurring within 31-days (Days 1-31) follow-up period after any dose will be presented by System Organ Class (SOC) and Preferred Term (PT) with 95% [Clopper](#) Pearson exact CI. Similar tabulation will be done for unsolicited AEs rated by maximum severity, for unsolicited AEs with causal relationship to vaccination as defined by the investigator.

Document : \quintiles.net\enterprise\Apps\sasdata\SASb\SAS\GSK\Infanrix\PPD \Biostatistics\Documentation\NSAP

Author: PPD Version Number: 1.0

Version Date: [07JAN2021]

Template No.: CS_TP_BS016 Revision 6

Reference: CS_WI_BS005

Effective Date: 02Dec2019

17.1.1.1. Assessment of Intensity

Severity is classified as mild/ moderate/ severe (increasing severity) AEs starting after the first dose of study treatment with a missing severity will not be accounted in the analysis of “Severe” AEs. If a subject report an AE more than once within that SOC/ PT, the AE with the worst-case severity will be used in the corresponding severity summaries.

17.1.1.2. Relationship to Study Medication

Relationship, as indicated by the Investigator, is classified as “Yes” if causally related to “Hexavalent vaccine” or “Prevenar 13”.

17.1.2. SERIOUS AEs

For each study treatment, the incidence rates (frequencies and percentages) of subjects with SAE occurring after the first study dose will be presented by System Organ Class (SOC) and Preferred Term (PT) with 95% Clopper Pearson exact CI. Similar tabulation will be done for SAE with causal relationship to vaccination as defined by the investigator; for fatal SAE and for causally related fatal SAE. Serious AEs will be recorded on the “Expedited Adverse Events” page of the eCRF.

17.1.3. UNSOLICITED AE, EXCLUDING SAEs

For each study treatment, the incidence rates (frequencies and percentages) of subjects with unsolicited AEs, excluding serious AE, occurring within 31-days (Days 1-31) follow-up period after any dose will be presented by System Organ Class (SOC) and Preferred Term (PT) without 95% Clopper Pearson exact CI. The number of events defined as the number of PT with different start date will be included in the summary. This summary is needed for web posting and will not be part of the study report. Unsolicited AEs excluding SAEs will be recorded on the “Non-Serious Adverse Events and Intercurrent Medical Conditions” pages of the eCRF.

Listings of AEs and SAEs leading to withdrawal of study treatment and AEs and SAEs leading to death will be provided.

17.2. VITAL SIGNS AND PHYSICAL EXAMINATION

The following vital sign measurements collected at Day 1 will be reported for this study:

Document : \quintiles.net\enterprise\Apps\sasdata\SASb\SAS\GSK\Infanrix\PPD \Biostatistics\Documentation\NSAP

Author: PPD Version Number: 1.0
Version Date: [07JAN2021]

Template No.: CS_TP_BS016 Revision 6 Reference: CS_WI_BS005

Effective Date: 02Dec2019

- Weight (kg)
- Height (cm)

A listing of this data will be provided. Descriptive statistics of the vital signs will be presented along with demographic characteristics.

APPENDIX 1. PROGRAMMING CONVENTIONS FOR OUTPUTS

IQVIA OUTPUT CONVENTIONS

Outputs will be presented according to the following IQVIA Output Conventions

Document Headers

All TFL is to include the following header:

GSK Vaccines
Vaccine: *Infanrix hexa*
Study 212645 (DTPa-HBV-IPV-141) - *DELIVERY DESIGNATION*

where delivery designation is the name of the current delivery, e.g., DRY-RUN, FINAL ANALYSIS REPORT, etc

DATES

Depending on data available, dates will take the form yyyy-mm-dd.

ATTRIBUTING EVENTS TO VACCINE DOSES

The dose relative to an event is the most recent study dose given to a subject prior to the start of a given event. For example, if the start date of an adverse event is between Dose 1 and Dose 2, the relative dose will be Dose 1. If an event starts on the same day as a study dose, the relative dose will be derived from the additional information provided in the case report form (CRF) using the contents of the flag indicating if the event occurred before or after study dose. If 'after study dose' is selected, the relative dose for the event will be the one administered on the start day of the event. If 'before study dose' is selected, the relative dose for the event will be the dose prior to this one.

ONSET DAY

The onset day for an event (e.g. AE, concomitant medication/vaccination) is the number of days between the last study dose and the start date of the event. This is 1 for an event occurring on the same day as a study dose (and reported as starting after study dose).

Document : \quintiles.net\enterprise\Apps\sasdata\SASb\SAS\GSK\Infanrix\PPD\Biostatistics\Documentation\NSAP

Author: PPD Version Number: 1.0

Version Date: [07JAN2021]

Template No.: CS_TP_BS016 Revision 6 Reference: CS_WI_BS005

Effective Date: 02Dec2019

SPELLING FORMAT

English UK.

PRESENTATION OF TREATMENT GROUPS

For outputs, treatment groups will be represented as follows and in the given order:

Vaccine Group	For Table, Listings and Figures
Infanrix hexa	Infanrix hexa
Vaxelis	Vaxelis
Prevenar 13	Prevenar 13

PRESENTATION OF VISITS

For outputs, visits will be represented as follows and in that order:

Long Name (default)	Short Name
Visit 1	V1
Visit 2	V2
Visit 3	V3
Visit 4	V4
Visit 5	V5

LISTINGS

All listings will be ordered by the following (unless otherwise indicated in the template):

- Vaccine group (or intervention received if it's a safety output),
- Center-subject ID,
- Date (where applicable),

Document : \quintiles.net\enterprise\Apps\sasdata\SASb\SAS\GSK\Infanrix\PPD\Biostatistics\Documentation\NSAP

Author: PPD Version Number: 1.0

Version Date: [07JAN2021]

Template No.: CS_TP_BS016 Revision 6

Reference: CS_WI_BS005

Effective Date: 02Dec2019

- Subjects without Hexavalent vaccine administered will appear in a treatment groups labeled 'Not vaccinated with Hexavalent vaccine.' in listings.

Document : \quintiles.net\enterprise\Apps\sasdata\SASb\SAS\GSK\Infanrix\PPD \Biostatistics\Documentation
Author: PPD Version Number: 1.0
Version Date: [07JAN2021]
Template No.: CS_TP_BS016 Revision 6 Reference: CS_WI_BS005
Effective Date: 02Dec2019

APPENDIX 2. PARTIAL DATE CONVENTIONS

Imputed dates will NOT be presented in the data listings.

When partially completed dates (i.e. with missing day or month) are used in calculations, the following standard rules will be applied:

- A missing day will be replaced by 15
- A missing day and month will be replaced by June 30th.

The following exceptions apply:

- Adverse event start dates with missing day:
 - If the event starts in the same month as at least one of the study doses, the contents of AE.AESTRTPT (the flag indicating if the event occurred before or after vaccination) will be used to complete the date. If 'after vaccination' is selected, the imputed start date will match the first (or only) study dose given during that month. If 'before vaccination' is selected, the imputed date will be one day before the first (or only) study dose given during that month.
- Adverse event start dates with missing day and month:
 - If the event starts in the same year as at least one of the study doses, the contents of AE.AESTRTPT (the flag indicating if the event occurred before or after vaccination) will be used to complete the date. If 'after vaccination' is selected, the imputed start date will match the first (or only) study dose given during that year. If 'before vaccination' is selected, the imputed date will be one day before the first (or only) study dose given during that year.

All other cases of incomplete AE or concomitant medication/vaccination start date will follow the standard rules above.

Document : \quintiles.net\enterprise\Apps\sasdata\SASb\SAS\GSK\Infanrix\PPD \Biostatistics\Documentation
n\SAP

Author: PPD Version Number: 1.0

Version Date: [07JAN2021]

Template No.: CS_TP_BS016 Revision 6

Reference: CS_WI_BS005

Effective Date: 02Dec2019

Approved By:	PPD	Refer to eSignature	PPD
Position:	Lead Scientific Writer		
Company:	GlaxoSmithKline Biologicals SA		

Document: \\quintiles.net\enterprise\apps\sasdata\SASb\SAS\GSK\Infanrix\PPD\Biostatistics\Documentation
ISAP

Author: PPD Version Number: 1.0
Version Date: [07JAN2021]

Template No.: CS_TP_BS016 Revision 6 Reference: CS_WI_BS005

Effective Date: 02Dec2019

Statistical Analysis Plan - Version 1.0 - 01-Apr-2021

Electronic Signature Manifestation

This page is a manifestation of the electronic signature(s) used in compliance with the organization's electronic signature policies and procedures.

Signer Full Name	Meaning of Signature	Date and Time

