## 8.3 Adverse Events

### 8.3.1 Time Period and Frequency for Collecting AE and SAE Information

All SAEs will be collected from Visit 1 through study end, at the time points specified in the SoA [[Table 3](#)].

All AEs will be collected from vaccination through the 31-day follow-up period after each vaccination, as specified in the SoA [[Table 3](#)].

Medical occurrences that begin before the start of study treatment but after obtaining informed consent will be recorded on the Medical History/Current Medical Conditions section of the eCRF, not the AE section.

All SAEs will be recorded and reported to the Sponsor or designee within 24 hours, as indicated in [Appendix 4](#). The investigator will submit any updated SAE data to the Sponsor within 24 hours of it being available.

Investigators are not obligated to actively seek AEs or SAEs after conclusion of the study participation. However, if the investigator learns of any SAE, including a death, at any time after a subject has been discharged from the study, and he/she considers the event to be reasonably related to the study treatment or study participation, the investigator must promptly notify the Sponsor.

The method of recording, evaluating, and assessing the causality of AEs and SAEs and the procedures for completing and transmitting SAE reports are provided in [Appendix 4](#).

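### Day-15 imputation of incomplete AE start dates has no bound at Day 31, so some AEs collected inside the 31-day window would be left out of the 31-day table

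*SAP*

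**What the plan says.** Protocol section 8.3.1 fixes the collection window: "All AEs will be collected from vaccination through the 31-day follow-up period after each vaccination". SAEs are collected throughout the study. SAP section 17.1.1 tabulates unsolicited AEs "occurring within 31-days (Days 1-31) follow-up period after any dose". SAP section 17.1.2 tabulates "subjects with SAE occurring after the first study dose", with no Day 31 limit. SAP Appendix 1 sets the onset-day count: "This is 1 for an event occurring on the same day as a study dose".

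SAP Appendix 2 governs incomplete dates used in calculations:

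- Standard rule: a missing day becomes the 15th; a missing day and month become 30 June.
- AE exception, missing day: if a dose was given in the same month, the before/after flag decides. An event flagged as after vaccination takes the dose date; one flagged as before takes the day preceding it.
- AE exception, missing day and month: the same logic applied to the year. "If 'before vaccination' is selected, the imputed date will be one day before the first (or only) study dose given during that year".
- Remainder: "All other cases of incomplete AE or concomitant medication/vaccination start date will follow the standard rules above".

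Listings show the date as recorded, not the imputed one.

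**The concern.** The month-matching exception covers an AE in the month of a dose. It does not cover an AE in the next month, although the 31-day window usually runs into that month. There the 15th is used whatever the dose date, and nothing stops it from falling after Day 31. For a non-serious AE recorded according to the protocol, such a date contradicts the collection rule, which already implies onset by Day 31.

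At stake is the unsolicited AE percentage, a secondary endpoint. The affected records would be left out of the table that reports it.

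The year-only rule raises a second, conditional question. It always uses the first dose of the year. If the flag was set against a later dose, the event is placed before an earlier dose, possibly before Dose 1.

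**Working it through.** The documents give no figure for this point, so there is none to reproduce. The check applies Appendix 2 literally.

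**Inputs.** Collection and table window: Days 1-31 (Protocol 8.3.1; SAP 17.1.1). Onset day = date difference + 1 (SAP Appendix 1). Missing day in a month without a dose: the 15th (SAP Appendix 2).

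**Example.** Dose on 10 January. Day 31 is 9 February, so a protocol-conforming non-serious AE recorded for February began on 1-9 February (Days 23-31). The imputed 15 February is 36 days after the dose, which is Day 37. The AE is not counted.

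**General form.** Take a dose on day d of a month with L days. The 15th of the next month is onset day L - d + 16, and the window covers the first d + 30 - L days of that month.

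| Month length | Condition for loss | Doses affected | Onset days lost per month |
|---|---|---|---|
| 31 | 47 - d > 31 | d = 2 to 15 | 1 + 2 + ... + 14 = 105 |
| 30 | 46 - d > 31 | d = 1 to 14 | 1 + 2 + ... + 14 = 105 |
| 28 | 44 - d > 31 | d = 1 to 12 | 3 + 4 + ... + 14 = 102 |

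**Size, assuming uniform dose dates over a 365-day year and uniform onset over Days 1-31.**

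- Combinations: 365 x 31 = 11,315.
- Lost: 7 x 105 + 4 x 105 + 102 = 1,257. Doses on 30 and 31 January, whose windows reach March, add 3. Total 1,260.
- Share of all in-window AEs with a missing day: 1,260 / 11,315 = 11.1%.
- In-window onsets in a month after the dose month: 7 x 465 + 4 x 465 + 462 = 5,577. Share lost: 1,260 / 5,577 = 22.6%.

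A full enumeration of the 11,315 cases gives the same counts. A run with three doses at nominal spacing (0, 60 and 304 days; 33,945 cases) also gives 11.1%. The overall share assumes that the flag is correct for AEs in the month of the dose; those are set to Day 1 and kept. The loss in the following month needs no assumption about the flag.

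**Which onsets are lost.** The first of the next month is onset day L - d + 2. At the largest affected d this is 31 - 15 + 2 = 18, 30 - 14 + 2 = 18 and 28 - 12 + 2 = 18. Every loss therefore has true onset on Days 18-31. By dose date, the loss averages 37-40% for doses on days 12-14 of the month and is zero for days 16-29.

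**With the first of the recorded month imputed instead,** 0 of the 11,315 cases leave the window.

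**Year-only dates.** Suppose doses on 10 January and 11 March, and an AE on 20 January recorded with the year only and flagged as before vaccination with the March dose in mind. Appendix 2 imputes 9 January, the day before Dose 1. The event then falls outside the 31-day table and, if serious, outside the SAE table. This result depends on which dose the flag refers to.

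**The case against.** The strongest objection is that little is at stake. Memory aids are reviewed after each dose, SAEs are reported within 24 hours and queries are issued before lock, so few start dates should be incomplete. Safety is descriptive and the rule treats both arms alike. Records stay in listings, and an SAE moved past Day 31 stays in the SAE table. All of this stands.

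The 11% also depends on uniform onset, which no document supports. The risks named in Protocol section 2.3, such as injection site reactions and fever, would be expected early, and no onset on Days 1-17 is lost. This stands too.

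Nor does the day-15 rule only remove events. SAEs are collected after Day 31 and also enter the 31-day table. In a uniform run with one dose, the rule moved 1,523 of 10,950 onsets on Days 32-61 (13.9%) into the window. So it should not be said that the conventions always lower the count. For non-serious AEs collected as the protocol requires, however, there are no later onsets to offset the loss.

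A reader might go further on year-only dates. Protocol section 8.3.1 says: "Medical occurrences that begin before the start of study treatment but after obtaining informed consent will be recorded on the Medical History/Current Medical Conditions section". From this one might infer that every AE-page event began after Dose 1, that a before flag must refer to a later dose, and that the rule removes every event it touches. The documents do not support that. Protocol Appendix 4 counts a condition first found after vaccination as an AE even if it may have predated the study, so a date before Dose 1 can be right. SAP Appendix 1 explains the flag only for events starting on a dose day, and the eCRF definition is not available.

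**Conclusion.** The point holds for AEs with a missing day in a month without a dose. For doses on about days 1-15 of a month, Appendix 2 can place an AE from the following month after Day 31, against the protocol's own collection window. Under the uniform assumption the loss is about 11% of in-window AEs with a missing day, and about 23% of those starting after the dose month; it is smaller if onsets cluster early. These are shares of partial-date records only. Their number is not stated and is probably small, so the effect on the reported AE percentages cannot be sized and is likely minor. The expected effect is undercounting, not bias between groups.

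The year-only issue is conditional on the meaning of the flag in the eCRF. This is a worthwhile correction of low severity.

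**What to change.** In SAP Appendix 2, add a rule for non-serious AE start dates with a missing day in a month without a dose: impute the later of the first day of the recorded month and the date of the most recent dose before that month. With no dose in the month, this is the first of the month. Keep the 15th for other variables. Limiting the rule to non-serious AEs avoids moving late SAEs into the 31-day table.

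For year-only AE dates flagged as before vaccination, check the eCRF definition. Where it shows that the flag refers to a later dose, anchor the event to the dose preceding that one. Do not ban dates before Dose 1 outright, because Protocol Appendix 4 allows conditions that predate vaccination to be AEs.

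The cost is a few lines of SAP text and code, with no change to data collection. AE percentages may rise slightly.
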